It is anticipated that unscheduled visits may be needed throughout the trial for evaluation and management of any aGvHD flare, worsening cytopenias, occurrence of serious infections, non-hematologic toxicities, graft failure, hematologic disease progression or relapse.

The core study ends after 24 weeks (approximately 6 months) after enrollment of the last subject into the Phase II, and the study will continue for up to a total of 2 years (i.e., 18 months of follow-up) to generate longer-term survival data.

Figure 3-2 Study Visit Schematic

*End of treatment occurs when patient discontinues treatment at any time. Safety follow up will occur 30 days after last dose.
Patient will continue the visit schedule even if treatment is discontinued early.

** See Section 3 for details

4 Rationale

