6.1.5 Treatment duration

The planned duration of aGvHD treatment is 24 weeks (approximately 6 months).

The Treatment Period for each patient will begin on Study Day 1 and continue until the end of Week 24, unless treatment change for any reason including treatment failure, e.g. aGvHD progression, mixed response, or no response, or aGvHD flare failure as defined in [Section 8.4.1.2](#), intolerable toxicity, death, or withdrawal from the study for other reasons occurs.

During the Treatment period, and beyond Day 28, patient's treatment will be managed according to their response as follows:

For patients with response at Day 28 (see [Table 8-3](#)):

- Patients responding to ruxolitinib will continue ruxolitinib until Day 56. These patients may be tapered off ruxolitinib as needed, starting no earlier than Day 56. The dose tapering strategy should be based on evaluation of the condition of the subject, current dosing regimen and the clinical judgment of the Investigator. (see [Section 6.1.5.1](#).)
- If a taper of ruxolitinib is considered appropriate, the taper should be completed no later than Week 24 unless prolonged tapering is indicated due to an aGvHD flare or other safety concern (see [Section 6.1.5.1](#)).

For patients with a lack of response at Day 28 (see [Table 8-3](#)):

- Patients must discontinue study treatment and be treated per Investigator's judgement. These patients will then enter the long-term follow-up period.

Patients responding to treatment will be tapered off immunosuppression (corticosteroids and CNI) as described in [Section 6.1.5.1](#).

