Pregnancy Test (urine)		S ⁵	S (monthly) ⁵							
acute GvHD staging	X	X								
aGvHD Response assessment			X	X	X	X				
Chronic GvHD assessment			X (Monthly)			X		X	X	X
Hematologic disease relapse/progression assessment		X	X	X	X	X		X	X	X
Second primary malignancy assessment		X	X	X	X	X		X	X	X
Graft Failure Assessment	X		X (Monthly)			X		X	X	X
Adverse Events		X (From screening until safety follow up)								
Treatment Acceptability and Palatability questionnaire ⁶		X (post dose)	X (Only week 4)	X (Only week 24)						
Study Treatment administration		X	X	X	X					

Period	Screening	Treatment ¹					Safety Follow-up	Long Term Follow-up ²		
Visit Name	Screening	Day 1	Week 1- Week 8 (Weekly)	Week 12- Week 24 (Monthly)	Week 28- Week 48 (only in the case of taper or aGvHD flare, monthly)	EOT (Week 24/Week 48) ³	Safety Follow-up visit	Month 12	Month 18	Month 24
Weeks	-4	1	1 to 8	12 to 24	28 to 48	48	0	53	78	105
Days	-28 to -1	1	7 to 56	84 to 168	196 to 336	-	Last dose [contact]
PK blood sampling		X (see Section 8.6.1.1)	X (See Section 8.6.1.1)	X (See Section 8.6.1.1)						
Survival Follow-up								X	X	X
Disposition						X				

^X Assessment to be recorded in the clinical database or received electronically from a vendor

^S Assessment to be recorded in the source documentation only

¹ From Day 1 to Week 24/End of Study Treatment (EOT) Weekly visits from Week 1 to Week 8 (Day 56) Monthly visit (every 28 days) after Day 56 until Week 24 or EOT, whichever occurs later

² (See [Section 9.1.5](#) for details)

³ EOT visit occurs when the patient discontinues study treatment. If EOT occurs before Week 24 the patient will still follow the visit schedule as planned and then continue to the follow up phase.

⁵ For applicable female patients only ([Section 8.5.5](#)). Per Investigator discretion, a serum pregnancy test can be performed in lieu of a urine pregnancy test.

⁶ Only for patients administered with oral pediatric formulation starting treatment Day 1 ([Section 8.6.3.1](#))

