aGvHD Flare is defined as any increase in signs or symptoms of aGvHD that is sustained for >24h after an initial response (CR or PR) and requires re-escalation of immunosuppressive therapy (e.g. corticosteroid, CNI and/or ruxolitinib dosing). While all aGvHD flares will be captured on study whether occurring during steroid, CNI, or ruxolitinib taper, only flares that fulfill either one the following criteria will be considered a failure of treatment:

1. Addition of new systemic therapy for aGvHD due to inability to taper corticosteroids below methylprednisolone 0.5 mg/kg/day (or equivalent <0.6 mg/kg/day of prednisone) for a minimum 7 days,
OR
2. Addition of new systemic therapy for aGvHD due to re-escalation of corticosteroids to methylprednisolone >2 mg/kg/day (or equivalent >2.5 mg/kg/day of prednisone).

aGvHD assessments will be performed by the treating team according to standard criteria ([Harris et al 2016](#)) as described in [Table 8-3](#). Disease assessments must continue per the schedule of visits weekly until Day 56, unless withdrawal of consent/ Opposition to use data/biological samples or death occurs, even in patients who are withdrawn from treatment unless consent for these assessments is specifically withdrawn.

At later time points after Day 56 after the start of the study treatment, signs and symptoms of cGvHD may be observed. cGvHD signs and symptoms may occur in up to 50% of patients based on published literature. Patients will be evaluated for any signs or symptoms of cGvHD and scored using NIH Consensus Criteria (Lee et al 2015) as described in [Section 16.2](#) (Appendix 2). Development of cGvHD signs or symptoms is not considered a treatment failure of aGvHD. Treatment of cGvHD will follow institutional standards of procedure and Investigator preference. Ruxolitinib must not be administered for treatment of cGvHD. For patients receiving ruxolitinib at the time of onset of cGvHD, ruxolitinib taper will follow guidelines per [Section 6.1.5.1](#).

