Patients who discontinue ruxolitinib study treatment for reasons other than achieving a CR or PR should NOT be considered withdrawn from the study and will enter the Long Term Follow-Up after completion of the Safety Follow Up visit [Section 9.1.5](#) and assessments at the end of Week 24. All other patients (including patients that discontinue ruxolitinib prior to Week 24 for achieving a CR or PR) will enter Long-term follow-up and continue to follow the Visit Evaluation Schedule as outlined in the [Table 8-1](#). Patients who develop cGvHD must discontinue from the study, and may utilize a ruxolitinib tapering strategy per [Section 6.1.5.1](#). Patients with hematologic disease progression, graft failure, AE, patient safety, or pregnancy may require abrupt cessation of ruxolitinib study treatment per Investigator discretion. Patients should return for assessments as specified at the EOT visit in [Table 8-1](#). The investigator must also contact the IRT to register the patient's discontinuation from study treatment.

If they fail to return for these assessments for unknown reasons, every effort (e.g. telephone, email, letter) should be made to contact them as specified in [Section 9.1.5](#).

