9.1.5 Follow up for safety evaluations

1. Safety Follow-up Visit

All patients must have a follow-up visit for safety evaluations 30 days (+ 3 day visit window) following the last dose of study treatment based on discontinuation from Treatment Period.

At the Safety Follow-Up visit, adverse events and therapies after treatment discontinuation will be reviewed. In addition, serum pregnancy will be collected for female patients of child-bearing potential. Refer to [Table 8-1](#). Patients who remain on ruxolitinib at Week 48 and obtain access to ruxolitinib outside of the study will not complete the safety follow-up visit since study treatment will continue.

1. Long-term safety Follow-up

All patients who discontinue study treatment (responders, non-responders, completing or prematurely discontinued from treatment period for any reasons as outlined above) will enter in the Long Term Follow-Up period, which lasts up to 24 months from start of study treatment (Day 1). Patients who prematurely discontinue ruxolitinib prior to Week 24 (without achieving CR or PR), must have assessments performed at the end of Week 24 ([Table 8-1](#)) and subsequently enter the Long Term follow-up period.

Visits are scheduled every six months (+/- 1 month from scheduled visit) starting Month 12 followed by subsequent visits at Month 18 and Month 24. Patients who may have an End of Treatment at Week 48 due to extended taper or aGvHD flare, will have the long-term follow up at Month 18 and 24 only.

Information to be collected during Long-Term follow-up is detailed in [Table 8-1](#). Data collected should be entered in the appropriate eCRF. Unscheduled visits may be performed as necessary. Additional assessments may be done as per institutional guidelines at investigator's discretion at any time during the trial.

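### The protocol gives conflicting assessment schedules after an early ruxolitinib stop, so detection of relapse, graft failure and chronic GvHD between Day 28 and Week 24 could depend on why the patient stopped

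*Protocol*

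**What the plan says.** Several parts of the protocol keep the full visit schedule after an early stop:

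- Table 8-1 footnote 3: "If EOT occurs before Week 24 the patient will still follow the visit schedule as planned and then continue to the follow up phase".
- The note to Figure 3-2: "Patient will continue the visit schedule even if treatment is discontinued early".
- Table 8-1 footnote 1 and section 3.3 run the four-weekly visits to Week 24 or end of treatment (EOT), whichever is later.

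Other parts describe less:

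- Section 9.1.1 first states "Patients who discontinue ruxolitinib study treatment for reasons other than achieving a CR or PR should NOT be considered withdrawn from the study". It adds that they "will enter the Long Term Follow-Up after completion of the Safety Follow Up visit" and the Week 24 assessments. All others, including those who stop early because of CR or PR, stay on the Table 8-1 schedule.
- Section 9.1.5 repeats the distinction: "Patients who prematurely discontinue ruxolitinib prior to Week 24 (without achieving CR or PR), must have assessments performed at the end of Week 24".
- Section 6.1.5 requires Day 28 non-responders to stop study treatment and continues: "These patients will then enter the long-term follow-up period". The first long-term visit is Month 12 (sections 3.3 and 9.1.5).

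Section 8.4.1.2 adds a partial safeguard, which extends to patients off treatment: "Disease assessments must continue per the schedule of visits weekly until Day 56".

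SAP 3.7.1 censors EFS, FFS, NRM, MR and cGvHD incidence at the last contact date. SAP 3.7.2 reports them at 1, 2, 6, 12, 18 and 24 months. SAP 3.7.3 covers only missing Day 14 response data.

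**The concern.** Section 9.1.1 makes the visit path depend on the reason for stopping, and section 6.1.5 makes it depend on Day 28 response. A site that followed either one literally would look less often for relapse, graft failure and chronic GvHD in patients who failed or stopped for toxicity than in patients who stopped in response.

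The 30-day safety visit does not fill the gap. In Table 8-1 it carries adverse events, medications and a pregnancy test, but no relapse, graft-failure or GvHD assessment.

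The SAP's censoring rule turns a missed assessment into event-free time. Under SAP 3.1.1 the last contact date can come from an adverse event, a medication record or a laboratory sample. A patient can therefore be carried as free of relapse well past the last relapse assessment. A death after an undetected relapse would be counted as NRM. No rule says how an event first found at Week 24 or Month 12 is dated.

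**Working it through.** The plan states no figure on this point, so there is none to reproduce. The check counts visits.

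**Inputs.** The patient stops at Day 28. Table 8-1 visits after that and before Month 12 are Weeks 5, 6, 7, 8 (Days 35, 42, 49, 56) and Weeks 12, 16, 20, 24 (Days 84, 112, 140, 168): 4 + 4 = 8. Month 12 is Day 365 (SAP 3.1.1).

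| Rule followed | Visits kept of 8 | Gaps before Day 365 | Kept if weekly visits to Day 56 (8.4.1.2) are added |
|---|---|---|---|
| Table 8-1 footnote 3, Figure 3-2 note | 8 | longest 365 − 168 = 197 days | 8 |
| Sections 9.1.1 and 9.1.5 | 1 (Week 24) | 168 − 28 = 140, then 197 days | 4 + 1 = 5 |
| Section 6.1.5 | 0 | 365 − 28 = 337 days | 4; longest gap 365 − 56 = 309 days |

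Relapse/progression is assessed at every visit in Table 8-1, so the count of 8 applies to it directly. Chronic GvHD and graft failure are marked monthly there, which leaves 5 (Weeks 8, 12, 16, 20, 24) under the full schedule. The last column covers aGvHD. It covers the other assessments only if the disease assessments in section 8.4.1.2, an aGvHD section, are meant to include them.

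**Patients concerned through Day 28 non-response alone, 45 × (1 − ORR).**
- Planning ORR of 80% (section 12.8.1): 45 × 0.20 = 9.
- Minimum of 33 responders (Table 12-2): 45 − 33 = 12.
- Historical 55% (section 12.8.1): 45 × 0.45 = 20.25, about 20.

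Patients who stop for toxicity add to the group under 9.1.1; the documents give no expected number.

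**Illustration, on assumptions not in the documents.** Events arise at a constant hazard from Day 28, are found only at scheduled visits and are dated when found. True 12-month incidence in the affected patients is 20% (range 10–40%).

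λ = −ln(1 − 0.20) / 337 = 0.000662 per day. Recorded incidence at time t = 1 − exp(−λ × (day of last visit by t − 28)).

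| Time | True | Table 8-1 | 9.1.1/9.1.5 | 6.1.5 |
|---|---|---|---|---|
| Month 2 (Day 61) | 2.2% (1.0–4.9) | 1.8% (0.9–4.2) | 0% | 0% |
| Month 6 (Day 183) | 9.8% (4.7–20.9) | 8.9% (4.3–19.1) | 8.9% (4.3–19.1) | 0% |
| Month 12 (Day 365) | 20% | 20% | 20% | 20% |

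The Week 24 visit (Day 168) precedes Month 6, so 9.1.1/9.1.5 loses nothing there against the full schedule. Spread over all 45 patients, the Month 6 shortfall under 6.1.5 is 0.20 × 8.9 = 1.8 percentage points at 80% ORR and 0.45 × 8.9 = 4.0 at 55%. If section 8.4.1.2 does cover relapse, the Month 2 shortfall disappears and 6.1.5 records 1.8% at Month 6.

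**Timing.** Amendment 3 reports enrolment complete as of 11 February 2021. Allowing 28 days of screening plus 168 days, the last Week 24 fell by about 26 August 2021. Amendment 3 uses a template dated 14 January 2022.

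**The case against.** The strongest reply is that the protocol already has the right rule and the other sections are only loosely worded. Section 3.3, Table 8-1 footnotes 1 and 3 and the Figure 3-2 note all keep the visits, and the opening of section 8 tells patients who stop treatment to attend visits as in the assessment schedule. Neither 9.1.1 nor 9.1.5 says that Week 24 is the only visit; both can be read as saying when long-term follow-up begins. Section 6.1.5 does not say that patients enter it at once.

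There are other routes to detection. Graft failure is also reported as an adverse event (8.4.1.4), starting treatment for relapse itself counts as relapse (Appendix 3), the safety visit reviews therapies started after stopping, and unscheduled visits are expected (3.3). A non-responder given new systemic aGvHD therapy around Day 28 has already failed for FFS. All these estimates are descriptive.

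This reduces the size but does not settle the rule. Section 9.1.1 contrasts two groups and gives the Table 8-1 schedule to only one of them. Section 6.1.5 lets treatment failure end the treatment period, and sections 8.4.1.3 and 8.4.1.5 tie chronic GvHD and relapse assessments to that period, EOT and long-term follow-up. A site could reasonably stop them at EOT.

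**Conclusion.** The conflict is in the current text and unresolved. If sites followed 6.1.5 or 9.1.1/9.1.5 literally, relapse, graft-failure and cGvHD assessment between Day 28 and Week 24 would depend on the reason for stopping: 0 or 1 of 8 visits against 8, apart from what 8.4.1.2 retains to Day 56. About 9 to 20 of 45 patients are concerned through non-response. The endpoints at risk are the relapse and graft-failure parts of EFS, the relapse part of FFS, the competing event in NRM, MR and cGvHD incidence. The effect falls chiefly on the 2-month estimate and on event timing; the 6-month estimate suffers only under the literal 6.1.5 reading. How large it is depends on site practice, which the documents do not show.

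A reader might infer more in three ways, none of them supported:

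- *That events are in fact ascertained by response status.* The rules contradict each other; they do not all apply, and one of them treats everyone alike. Section 9.1.1 also splits by reason for stopping, so a Day 28 responder who stops for toxicity falls in the reduced group.
- *That the imbalance lasts to Month 12.* Visits at Weeks 28 to 48 exist only for extended taper or flare, so patients off treatment have none between Week 24 and Month 12 under any rule.
- *That durable ORR at Day 56 is compromised.* Section 8.4.1.2 keeps weekly assessments to Day 56 off treatment, and a Day 28 non-responder is already a failure for that endpoint. Day 28 ORR and OS are not affected either.

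**What to change.** **Protocol.** Reconcile sections 3.3 (with the Figure 3-2 note), 6.1.5, 8 (opening text and Table 8-1 footnotes), 8.4.1.2, 9.1.1 and 9.1.5 into one assessment rule: every early stopper, whatever the reason, keeps the Table 8-1 off-treatment assessments to Week 24 and then enters long-term follow-up, as footnote 3 already states. State whether the disease assessments in 8.4.1.2 include relapse, graft failure and cGvHD. This concerns assessment visits only, not when treatment stops.

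**SAP 3.7.** On the dates above, the Day 28 to Week 24 window had probably closed for every patient before Amendment 3, so this is the part that can still change the results:

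- tabulate, by reason for stopping, how many patients had relapse, graft-failure and cGvHD assessments between EOT and Week 24;
- state how an event first found at Week 24 or Month 12 is dated;
- present the EFS, MR and cGvHD estimates with that coverage beside them.

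The cost is protocol wording, one extra listing and, where any are still possible, some off-treatment visits that Table 8-1 already contains.

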Study treatment	Any drug administered to the study patients as part of the required study procedures; includes investigational drug (s), control(s) or non-investigational medicinal product(s)
Study treatment discontinuation	When the subject permanently stops taking study treatment prior to the defined study treatment completion date
Subject	An individual who has consented to participate in this study (or has been consented by a legal representative).
Subject number	A number assigned to each subject who enrolls in the study. When combined with the center number, a unique identifier is created for each subject in the study.
Treatment Arm/Group	A treatment arm/group defines the dose and regimen or the combination and may consist of 1 or more cohorts.
Variable	Information used in the data analysis; derived directly or indirectly from data collected using specified assessments at specified timepoints.
Withdrawal of consent (WoC)/Opposition to use data/biological samples	Withdrawal of consent from the study occurs when the patient explicitly requests to stop use of their data and biological samples (opposition to use data and biological samples) AND no longer wishes to receive study treatment AND does not agree to further required assessments. This request should be in writing (depending on local regulations) and recorded in the source documentation. Opposition to use data/biological samples occurs in the countries where collection and processing of personal data is justified by a different legal reason than consent.

Amendment 3

Amendment rationale

As of 11Feb2021, CINC424F12201 completed enrollment with a total of 45 patients, which included 29% treatment-naïve patients and 71% SR-aGvHD patients. Treatment by Group consisted of 18 patients in Group 1 (age ≥ 12 y to < 18 y), 12 patients in Group 2 (age ≥ 6 y to < 12 y) and 15 patients in Group 3 (age ≥ 2 y to < 6 y).

The main purpose of this amendment to include public health emergency disruption proofing language, to provide guidance on patient management, including withdrawal of consent, and to decrease the minimum enrollment requirement of treatment-naïve patients from 40% to at least 20% due to recruitment challenges. The sample remains representative of the study population and therefore the sample size was not re-estimated due to this modification.

Changes to the protocol

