3.3 Study periods

The study is comprised of the following periods:

- **Screening Period (Day -28 to Day -1)**

Patients diagnosed with treatment-naïve or steroid refractory aGvHD will have screening activities and assessment of inclusion and exclusion criteria once the study informed consent is obtained. Upon confirmation of eligibility, the patients will be enrolled to the study.

- **Treatment Period (Day 1 to Week 24)**

Study treatment will begin on Day 1. Subjects meeting eligibility requirements will be treated with ruxolitinib plus corticosteroids +/- CNI for 24 weeks (approximately 6 months) unless discontinuation criteria (See [Section 9.1.1](#)) or withdrawal from the study for other reasons occurs. Dose modifications are allowed for safety. Patients that have not discontinued ruxolitinib by the end of Week 24 or experience aGvHD flare may continue to receive treatment for a maximum of 48 weeks (See [Section 6](#) for treatment details and dose modifications). In this case, the end of treatment for such patients will extend beyond Week 24 but MUST end by Week 48.

Study visits will occur per the following schedule to monitor tolerability and efficacy of the study treatments during the Treatment period:

- Weekly visits from Day 1 up to Day 56;
- Visits every 4 weeks beyond Day 56 and until Week 24 or End of Treatment (EOT), whichever occurs later.

A 30-day safety follow-up visit will be done for all patients after the last dose of ruxolitinib.

- **Long-term follow-up Period (From EOT to Month 24)**

[figure not shown]
Recognizing that aGvHD is a complication of alloSCT that often leads to death within 2 years after the procedure, and that assessment of long-term safety and durable efficacy is clinically meaningful, all patients (responders and non-responders in both arms, regardless of when treatment was discontinued) will be followed to collect long term data including: survival, any relapse/progression of the underlying hematologic disease for which the alloSCT procedure was performed (refer to [Section 16.3](#) Appendix 3), NRM, any occurrence of graft failure, EFS, any occurrence of cGvHD, and occurrence of any second primary malignancies.

Visits will be performed at 12, 18, and 24 months from the start of treatment (Day 1).

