9.1 Discontinuation from study treatment and from study

9.1.1 Discontinuation of study treatment

Patients may voluntarily discontinue from the study treatment for any reason at any time. If a patient decides to discontinue from the study treatment the investigator should make a reasonable effort (e.g. telephone, e-mail, letter) to understand the primary reason for this decision and record this information in the patient's chart and on the appropriate CRF pages. They may be considered withdrawn if they state an intention to withdraw, fail to return for visits, or become lost to follow-up for any other reason.

The investigator may discontinue study treatment for a given patient if, he/she believes that continuation would be detrimental to the patient's well-being.

In addition to mandatory discontinuation from study treatment listed in [Table 6-3](#), discontinuation from study treatment is required under any of the following circumstances:

1. Lack of response of aGvHD treatment at Day 28 ([Section 6.1.5](#)) ([Section 12.4.1](#))
2. Patients requiring new systemic therapy for aGvHD at any time ([Section 6.1.5.1.1](#))
3. aGvHD flare occurring during ruxolitinib taper after Week 24 ([Section 6.1.5.1.1](#))
4. Development of signs or symptoms of cGvHD including *de novo*, overlap, or progressive onset ([Section 8.4.1.3](#))
5. Underlying hematological disease progression or relapse ([Section 8.4.1.5](#))
6. Evidence of graft failure necessitating rapid taper of immunosuppression, administration of non-scheduled DLI, stem cell boost, chemotherapy, or other treatment that would expectedly affect aGvHD,
7. Adverse events leading to discontinuation from study treatment ([Section 6.5.2](#))
8. Pregnancy ([Section 8.5.5](#))
9. Protocol deviation that results in a significant risk to the patient's safety including use of prohibited treatment ([Section 6.2.2](#))
10. Patient has not weaned off corticosteroids, CNIs and ruxolitinib by Week 48 ([Section 6.1.5.1](#).)

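### Protocol 9.1.1 says that cGvHD ends study participation, which contradicts its own paragraph and the sections that follow every patient to Month 24

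*Protocol*

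**What the plan says.** The sentence at issue is in Protocol Section 9.1.1, whose title concerns stopping study treatment: "Patients who develop cGvHD must discontinue from the study, and may utilize a ruxolitinib tapering strategy per" Section 6.1.5.1. It is current protocol text, not part of an amendment summary.

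The surrounding text says otherwise:

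- **Same paragraph, first sentence.** The rule for patients who stop ruxolitinib without a complete or partial response as the reason is that they "should NOT be considered withdrawn from the study and will enter the Long Term Follow-Up after completion of the Safety Follow Up visit".
- **Section 9.1.1, numbered list.** The lead-in is "discontinuation from study treatment is required under any of the following circumstances", and item 4 is "Development of signs or symptoms of cGvHD including" de novo, overlap or progressive onset. So cGvHD is listed as a reason to stop treatment.
- **Section 3.3.** All patients, whenever treatment stopped, "will be followed to collect long term data including: survival, any relapse/progression of the underlying hematologic disease", and also for NRM, graft failure, EFS, cGvHD and second malignancies.
- **Section 6.5.2.1.2.** Everyone who completes or stops treatment is followed until two years from Day 1.
- **Section 9.1.5.** Everyone who stops treatment, for any of the reasons outlined, enters long-term follow-up to Month 24.

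On frequency, Section 8.4.1.2 says that "cGvHD signs and symptoms may occur in up to 50% of patients based on published literature". The Amendment 3 rationale reports that the trial "completed enrollment with a total of 45 patients".

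**The concern.** Leaving treatment and leaving the study have different procedures in this protocol. Under Section 8, a patient who stops treatment has an end-of-treatment visit and then attends the follow-up visits, while a patient who leaves the study has a final evaluation visit. The glossary entry for premature withdrawal says that nothing further is planned after exit. Amendment 3 states that Section 9.1.1 was revised to separate the two ideas, and Section 9.1.2 stresses recording them accurately. A site could therefore take the words at face value: this is the only sentence in the paragraph specific to cGvHD, and it is mandatory.

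A site that did so would stop collecting survival, relapse, graft failure and second malignancies in these patients. SAP Section 3.7.1 censors OS, EFS, NRM and MR at the last date known alive, which would then fall near cGvHD onset. The SAP has no rule or sensitivity analysis for study exit at cGvHD. If cGvHD is related to later death or relapse, that censoring is informative.

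**Working it through.** **Which reading the text supports**

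| Text | Does cGvHD end the study? |
|---|---|
| 9.1.1, disputed sentence | Yes, if literal |
| 9.1.1, same sentence, taper clause | No: ruxolitinib may still be tapered, whereas the glossary has all study drug stopped at premature withdrawal |
| 9.1.1, first sentence of paragraph | No |
| 9.1.1, list item 4 | No: a reason to stop treatment |
| 3.3, 6.5.2.1.2, 9.1.5 | No: follow-up to Month 24 for all |

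One clause points to study exit and everything else points away from it.

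**Patients affected under the literal reading**

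The 50% is a literature ceiling and cannot be re-derived from the documents. 0.50 × 45 = 22.5, so at most about 22 patients. At assumed rates of 20% and 40% the counts are 9 and 18. Each patient loses only the follow-up after onset.

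**Shift in 24-month OS: closed form**

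Assumptions, none of them from the documents: a death hazard of 3% per month to month 6; a share c of month-6 survivors develop cGvHD, all at month 6; monthly hazards afterwards are h_c with cGvHD and h_n without.

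- S(6) = exp(−0.03 × 6) = 0.835, so 45 × 0.835 ≈ 38 are at risk. With c = 0.5 about 19 remain after censoring.
- True OS24 = S(6) × [c·exp(−18h_c) + (1−c)·exp(−18h_n)]
- Kaplan-Meier with censoring at cGvHD = S(6) × exp(−18h_n)
- Difference = S(6) × c × [exp(−18h_n) − exp(−18h_c)]

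exp(−0.18) = 0.835, exp(−0.36) = 0.698, exp(−0.54) = 0.583.

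| c | Later monthly hazards | Absolute shift in OS24 |
|---|---|---|
| 0.5 | equal | 0 |
| 0.5 | 1% vs 2% | 0.835 × 0.5 × (0.835 − 0.698) = 0.057 |
| 0.5 | 1% vs 3% | 0.835 × 0.5 × (0.835 − 0.583) = 0.105 |
| 0.3 | 1% vs 3% | 0.835 × 0.3 × (0.835 − 0.583) = 0.063 |

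In the 1% vs 3% case with c = 0.5, true OS24 is 0.592. The censored estimate is 0.487 if patients with cGvHD have the lower hazard, and about 0.697 if they have the higher one.

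**Shift and precision: simulation**

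Settings: N = 45; 24-month OS without cGvHD of 30%, 50% or 70%; half of patients susceptible, with onset uniform over months 2 to 12; hazard multiplied by 0.5, 1 or 2 after onset; 1,500 runs each.

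| OS24 without cGvHD | Shift, ratio 0.5 | Shift, ratio 2 | SE at ratio 1, full vs censored | At risk at Month 24, ratio 1 |
|---|---|---|---|---|
| 30% | 0.299 − 0.382 = −0.083 | 0.302 − 0.214 = +0.088 | 0.067 vs 0.093 | 13.4 vs 6.7 |
| 50% | 0.500 − 0.569 = −0.069 | 0.499 − 0.406 = +0.093 | 0.073 vs 0.099 | 22.5 vs 11.3 |
| 70% | 0.699 − 0.748 = −0.049 | 0.702 − 0.623 = +0.079 | 0.069 vs 0.093 | 31.5 vs 15.7 |

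With 20% susceptible, the shifts at ratios 0.5 and 2 shrink to between 2.0 and 3.9 points. At ratio 1 there is no material shift, but the standard error still rises.

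**The case against.** The strongest reply is that no careful reader would act on this sentence. The section title, the list, the opening of the paragraph and three other sections all say that the patient stays in follow-up, and the taper clause makes literal exit self-contradictory. On that view a word was left out and no data are at risk. The account of intent stands. It does not remove the contradiction, because the protocol attaches different procedures to the two kinds of discontinuation and this mandatory sentence names the wrong one.

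Three stronger readings are tempting, and the documents do not support them:

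- *That the plan ends survival follow-up for up to half of patients, as a design choice.* The design is follow-up to Month 24 for all. The loss arises only where a site applies the sentence literally, and 50% is a published upper figure for signs and symptoms, not a rate expected in this trial.
- *That 24-month OS would be wrong by about 10 points.* That needs a threefold hazard ratio and onset in half of survivors, all at month 6. The documents say nothing about whether cGvHD raises or lowers mortality, so neither size nor sign is known, and zero is within the range.
- *That the Month 12, 18 and 24 cGvHD assessments in Section 8.4.1.3 disprove exit at onset.* They look for occurrence of cGvHD, so patients who have not yet had it need them in any case.

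Reach is also limited. Day 28 ORR is largely unaffected, DOR and FFS already treat cGvHD onset as a competing risk, and the affected endpoints are descriptive, with no hypothesis tested.

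**Conclusion.** The sentence is wrong as written and should be corrected. It is an inconsistency of wording, and confidence in that is high.

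The consequence is conditional. Where a site followed the sentence, OS, EFS, NRM and MR would be censored around cGvHD onset, and graft failure and second malignancies would go unobserved afterwards. At the 50% ceiling this reaches at most about 22 of 45 patients. The shift in 24-month OS runs from 0 to about 10 points in either direction across the assumed hazards. With no shift at all, its standard error would still rise from about 0.07 to between 0.09 and 0.10. These figures assume that every site reads the sentence literally. The documents do not show that any site did, or whether follow-up is still running.

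**What to change.** Reword the sentence in Section 9.1.1 to say that onset of cGvHD does not end study participation or long-term follow-up, in line with Sections 3.3, 6.5.2.1.2 and 9.1.5 and with the list in 9.1.1. Wording it in terms of participation keeps the correction clear of any treatment rule. How ruxolitinib is handled at cGvHD onset is described in Sections 6.1.5.1.1, 8.4.1.2 and 9.1.1, and the sponsor should reconcile those passages separately.

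If follow-up is still running, send sites a short clarification. In any case, report in the clinical study report how many patients left the study at cGvHD and their censoring times, so that readers can judge the OS, EFS, NRM and MR estimates.

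The cost is one phrase in the protocol, possibly a site letter, and one small disposition summary. Follow-up already lost may not be recoverable.
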